### 3.0 PATIENT SELECTION

For questions regarding eligibility criteria, see the Study Resources page. Please note that the Study Chair cannot grant waivers to eligibility requirements.

#### 3.1 On-Study Guidelines

This clinical trial can fulfill its objectives only if patients appropriate for this trial are enrolled. All relevant medical and other considerations should be taken into account when deciding whether this protocol is appropriate for a particular patient. Physicians should consider the risks and benefits of any therapy, and therefore only enroll patients for whom this treatment is appropriate.

Physicians should consider whether any of the following may render the patient inappropriate for this protocol:

- Psychiatric illness which would prevent the patient from giving informed consent.
- Medical condition such as uncontrolled infection, uncontrolled diabetes mellitus or cardiac disease which, in the opinion of the treating physician, would make this protocol unreasonably hazardous for the patient.
- Patients with a “currently active” second malignancy other than non-melanoma skin cancers or cervical carcinoma in situ. Patients are **not** considered to have a “currently active” malignancy if they have completed therapy and are free of disease for  $\geq 3$  years, had a gastric or bowel carcinoid  $\leq 1$  cm, or DCIS /LCIS of the breast without invasive cancer, or endometrial dysplasia/carcinoma in situ.
- Patients are **not** considered to have a “currently active” malignancy if they had a sebaceous neoplasm (sebaceous adenoma, sebaceous epithelioma, sebaceous adenocarcinoma, keratoacanthoma, and squamous cell carcinoma) that was noninvasive.

In addition:

- Women and men of reproductive potential should agree to use an appropriate method of birth control throughout their participation in this study due to the teratogenic potential of the therapy utilized in this trial. Appropriate methods of birth control include abstinence, oral contraceptives, implantable hormonal contraceptives, or double barrier method (diaphragm plus condom). For women, birth control should begin at least 28 days prior to the start of therapy and continue for 5 months after completion of therapy. For men, birth control should begin prior to registration and continue for 5 months after completion of therapy.

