**3.2.6 Not Pregnant and Not Nursing**

This study involves: 1) an investigational agent whose genotoxic, mutagenic and teratogenic effects on the developing fetus and newborn are unknown; and 2) an agent that has known genotoxic, mutagenic, and teratogenic effects.

Therefore, for women of childbearing potential only, a negative pregnancy test done  $\leq$  7 days prior to registration is required.

A female of childbearing potential is a sexually mature female who: 1) has not undergone a hysterectomy or bilateral oophorectomy; or 2) has not been naturally postmenopausal for at least 12 consecutive months (i.e. has had menses at any time in the preceding 12 consecutive months).

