**8.1.4 Antiemetics may be used at the discretion of the attending physician, with the exception of steroids above.**

As this regimen has high emetogenic potential, it is recommended that all subjects on study should receive an aggressive prophylactic antiemetic regimen, consisting of a 5HT-3 antagonist +/- NK1 antagonist. Steroids are permitted for antiemetic prophylaxis during mFOLFOX6 chemotherapy, but must be limited to a maximum of equivalent dexamethasone 10 mg daily for 2 days every 14 days, see [Section 8.1.12](#) below for additional details.

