Female patients of childbearing potential should utilize contraception and take active measures to avoid pregnancy while undergoing atezolizumab treatment and for at least 150 days after the last dose of atezolizumab.

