## Contraception

### HIGHLY EFFECTIVE METHODS OF CONTRACEPTION

- Hormonal methods of contraception, including oral contraceptive pills\* (combination of estrogen and progesterone), vaginal ring, injectables, implants and intrauterine devices (IUDs) **\*NOTE: Due to the increased GI toxicity (nausea, vomiting, diarrhea) oral contraceptives must be combined with an additional method of contraception (e.g. a barrier method).**
- Nonhormonal IUDs, such as ParaGard®
- Bilateral tubal ligation
- Vasectomy
- Complete abstinence if it is the patient's preferred and usual lifestyle regardless of trial participation\*

\*Complete abstinence is defined as complete avoidance of heterosexual intercourse and is an acceptable form of contraception for all IMPs. Subjects who choose complete abstinence are not required to use a second method of contraception. Acceptable alternate methods of highly effective contraception should be discussed in the event that the subject chooses to forego complete abstinence.

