### UNACCEPTABLE METHODS OF CONTRACEPTION

- Oral contraceptive pill alone
- Diaphragm with spermicide
- Cervical cap with spermicide
- Vaginal sponge
- Condom
- Withdrawal (coitus interruptus)
- Progestin only pills by WOCBP subject or male subject's WOCBP partner
- Periodic abstinence (calendar, symptothermal, post-ovulation methods)

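### Section 3.1 accepts the pill with no second method and ends contraception at 5 months, where the trial's own German appendix requires a second method and 6 months after mFOLFOX6

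*Combined protocol and SAP*

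**What the plan says.** **Main protocol, section 3.1 (On-Study Guidelines).** On method: "Appropriate methods of birth control include abstinence, oral contraceptives, implantable hormonal contraceptives, or double barrier method (diaphragm plus condom". No second method is attached to the pill. On duration, women and men alike are to "continue for 5 months after completion of therapy", whichever arm they are in. The end of therapy is not defined as the last dose or the end of the last cycle. An opening sentence asks for contraception "throughout their participation in this study due to the teratogenic potential of the therapy utilized in this trial".

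**Main protocol, elsewhere.** Section 3.2.6 separates an investigational agent of unknown reproductive effect from "an agent that has known genotoxic, mutagenic, and teratogenic effects". The only drug-specific contraception period is in the nursing guidelines of section 10.5, for women: "for at least 150 days after the last dose of atezolizumab". Sections 10.2 to 10.4 state none for fluorouracil, leucovorin or oxaliplatin. Section 8.1.4 introduces its antiemetic advice with "As this regimen has high emetogenic potential".

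**German appendix (Appendix IV, AIO-GSA), section 4.3.2.** Because of gut toxicity, "oral contraceptives must be combined with an additional method of contraception (e.g. a barrier method", and the list of unacceptable methods opens with "Oral contraceptive pill alone". Women are to continue for 5 months from the final atezolizumab dose and 6 months from the final mFOLFOX6 dose. Men have the same two periods joined by an or. AIO-GSA 2.3.3 also gives a period of up to 6 months for fluorouracil, for both sexes.

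**The concern.** One protocol gives two answers for the same drugs, and the answer for most of the trial is the less cautious one. The appendix's objection to the pill is that vomiting and diarrhea make it unreliable. That follows from the regimen and not from German law. The 6 months are attached to mFOLFOX6 and fluorouracil, which every patient in both arms is assigned. The period in section 3.1 is close to the 150 days given for atezolizumab, a drug that Arm 2 never receives.

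What is at stake is fetal exposure to treatment that the protocol itself describes as teratogenic. A woman outside Germany who follows section 3.1 could rely on the pill alone through up to 12 cycles of mFOLFOX6. An Arm 2 patient could stop contraception some weeks before the only period these documents tie to mFOLFOX6.

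**Working it through.** The plan gives no figure to reproduce, so the check compares the texts and then does calendar arithmetic.

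**Same treatment?** AIO-GSA 2.3 to 2.5 send German sites to protocol sections 7.1 and 7.2 for dosing. The drugs and doses are the same.

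**Method.** Section 3.1 accepts the pill without qualification; AIO-GSA 4.3.2 rejects it alone. The main text supports the appendix's premise. Section 8.1.4 calls the regimen highly emetogenic, and sections 10.2 and 10.4 list nausea, vomiting and diarrhea among toxicities above 10% for fluorouracil and oxaliplatin. The reason covers a patient taking the pill herself, during treatment and while gut toxicity lasts. It does not extend to the months after recovery or to a male patient's partner.

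**Which drug should set the period?** In section 3.2.6 the investigational agent is the one with unknown effects. By elimination, the agent with known effects belongs to mFOLFOX6, which is all that Arm 2 receives. The periods that the documents tie to mFOLFOX6 or fluorouracil are those in AIO-GSA 4.3.2 and 2.3.3, both stated as 6 months.

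**Size of the gap.** Inputs: 5 months (section 3.1); 6 months after mFOLFOX6 and 5 months after atezolizumab (AIO-GSA 4.3.2); 14-day cycles (section 7.0); 13 monotherapy cycles (section 7.1). One month = 365.25/12 = 30.44 days, so 5 months = 152.2 days and 6 months = 182.6 days.

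Let t be the days from the last mFOLFOX6 dose to the last atezolizumab dose, with t = 0 for Arm 2. Let c = 0 if therapy ends at the last dose, or 13 if it ends on the last day of that 14-day cycle.

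- End under section 3.1 = max(0, t) + c + 152.2
- End under the appendix = max(182.6, t + 152.2)
- Gap = appendix end minus section 3.1 end, or 0 if negative

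| Case | Gap from last dose (c = 0) | Gap from end of cycle (c = 13) |
|---|---|---|
| Arm 2, or Arm 1 with t ≤ 0 | 182.6 − 152.2 = 30.4 days | 182.6 − 165.2 = 17.4 days |
| Arm 1, t = 14 | 182.6 − 166.2 = 16.4 | 182.6 − 179.2 = 3.4 |
| Arm 1, t = 28 | 182.6 − 180.2 = 2.4 | 0 |
| Arm 1 full course, t = 13 × 14 = 182 | 334.2 − 334.2 = 0 | 0 |

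The gap closes once t exceeds 30.4 days (c = 0) or 17.4 days (c = 13). Actual calendar months, run over every last-dose date from 2018 to 2023, give 28 to 31 days for Arm 2 from the last dose. From the end of the cycle they give 15 to 18 days counting 13 days on, or 14 to 17 counting 14.

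Taking the later of the two periods follows from the women's clause in AIO-GSA 4.3.2. For men it is an assumption, because that clause does not say which period governs when both drugs were given.

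**Could it still matter?** AIO-GSA 1.5 plans the last German treatment for February 2023. Adding 183 days to 28 February 2023 gives 30 August 2023. The reporting table in section 9.3.1 is dated 30 August 2024, 366 days later. To be inside a 6-month window on that date, a patient would need a last dose after about 29 February 2024. Treatment status outside Germany is not stated.

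**The case against.** The strongest reply is that this is a regional difference and not a flaw. The appendix's preface describes it as holding regulatory provisions and clarifications for Germany, its contraception text is marked as a supplement, and its fluorouracil rule sits beside a reference to the European product label. That stands against any claim of contradiction: German sites have a clear rule, and no document says that 5 months or the pill alone is wrong elsewhere. It does not answer why gut toxicity should count in one country only.

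Sections 10.2 to 10.4 refer readers to the package inserts for current safety information, and a model consent form exists. Neither can be seen here. A reader might infer that patients outside Germany are being told the pill alone is enough; the documents do not support that, because what those patients are told cannot be fully checked.

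Section 3.1 is also guidance. Its list of methods need not be exhaustive, an investigator may advise a second method, and section 8.1.4 recommends strong antiemetic prophylaxis. These points soften the concern. Antiemetics do not deal with diarrhea, and German patients have the same section 8 guidance yet still need a second method.

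On duration, the opening sentence of section 3.1, read literally, would cover the 8 years of follow-up in section 12.4 and leave no gap. The sentences that follow set the specific 5-month stop, which is what a site would apply. The fluorouracil wording in AIO-GSA 2.3.3 can be read as a ceiling; the women's rule in 4.3.2 cannot.

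Finally, the appendix is not a clean benchmark. It also rejects condoms, and diaphragms with spermicide, and its periods for partner pregnancies differ between passages (7 months for telling the investigator, 6 for follow-up). The point here is limited to two differences and is not a case for importing the appendix whole.

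**Conclusion.** The point holds as a low-severity improvement. For the same drugs and doses, section 3.1 is less protective than the trial's own appendix on pill use during treatment. On duration it is shorter by about one month, or about two weeks from the end of the last cycle. The duration difference applies to Arm 2 and to Arm 1 patients whose atezolizumab ends before, or within about a month after, the last mFOLFOX6 dose; on the end-of-cycle reading it disappears after about 17 days. Full-course Arm 1 has no duration gap.

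A reader might infer that section 3.1 is in error. The documents show only that two regional texts differ and that the reasons for the stricter one travel. A reader might also try to derive a number of patients at risk from the planned enrolment table in section 13.8. That table says nothing on childbearing potential or pill use, so no number is claimed.

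The conclusion rests on the 5-month sentences governing over the opening sentence of section 3.1 and, for men, on the later-of-two reading. It has no bearing on the statistical design.

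**What to change.** First establish whether any patient is on treatment or within 6 months of the last dose. If none is, record that the change has no practical effect. Otherwise amend section 3.1 for all sites along these lines:

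- Women using oral contraceptives add a second method, such as a barrier method, at least during treatment and while nausea, vomiting or diarrhea persists.
- Contraception runs to the later of 6 months from the final mFOLFOX6 dose and 5 months from the final atezolizumab dose. This replaces the undefined end of therapy and the conflicting whole-participation sentence.
- The sponsor's safety physician confirms the periods, in particular the rule for men, and the package inserts and consent form are checked against them.

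On the working above, this brings the gap to 0 days in every case. The cost is a wording change and a site memo. For patients it means a second method for pill users, and up to about one extra month of contraception in Arm 2 and for the Arm 1 early stoppers described above.

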#### 3.2 Eligibility Criteria

When calculating days of tests and measurements, the day a test or measurement is done is considered Day 0. Therefore, if a test were done on a Monday, the Monday one week later would be considered Day 7.

##### 3.2.1 Documentation of Disease

Histologically proven stage III colon adenocarcinoma (any T [Tx, T1, T2, T3, or T4], N1-2M0; includes N1C). Tumors must be deemed to originate in the colon including tumors that extend into/involve the small bowel (e.g. those at the ileocecal valve).

**DNA Mismatch Repair (MMR) Status:** Presence of deficient (d) DNA mismatch repair (dMMR). MMR status must be assessed by immunohistochemistry (IHC) for MMR protein expression (MLH1, MSH2, MSH6, PMS2) where loss of one or more proteins indicates dMMR.

dMMR may be determined either locally or by site-selected reference lab.

**Note:** loss of MLH1 and PMS2 commonly occur together.

FFPE tumor tissue is required for subsequent retrospective central confirmation of dMMR status.

Patients with testing that did not show dMMR (loss of MMR protein) are not eligible to participate. Patients whose tumors show MSI-H by PCR-based assay are not eligible to participate unless they also have MMR testing by IHC and are found to have dMMR (i.e. loss of one or more MMR proteins).

Patients who are known to have Lynch Syndrome, have been found to carry a specific germline mutation in an MMR gene (*MLH1*, *MSH2*, *MSH6*, *PMS2*), and have been shown to be dMMR by IHC are eligible to participate.

### 3.2.2 Disease Status

Tumors must have been completely resected. In patients with tumor adherent to adjacent structures, en bloc R0 resection must be documented in the operative report or otherwise confirmed by the surgeon. Near or positive radial margins are acceptable so long as en bloc resection was performed. Proximal or distal margin positivity is not permitted.

Entire tumor must be in the colon (rectal involvement is an exclusion). Surgeon confirmation that entire tumor was located in the colon is required only in cases where it is important to establish if the tumor is a colon vs. rectal primary. Patients with more than one primary colon adenocarcinoma are eligible if the qualifying stage III tumor is confined to the colon, and not rectum, and the other cancers of lower stage are removed in the en bloc R0 resection.

Based upon the operative report and other source documentation, the location of the primary tumor will be categorized as proximal or distal to the splenic flexure (included with distal), and further categorization will be as follows: cecum/ascending, transverse, descending, sigmoid colon, or rectosigmoid colon.

No evidence of residual involved lymph node disease or metastatic disease at the time of registration based on clinician assessment of imaging. The treating physician will determine if incidental lesions on imaging require workup to exclude metastatic disease. If based on review of images, the treating physician determines the patient to be stage III, then the patient is eligible.

### 3.2.3 Prior Treatment

No prior medical therapy (chemotherapy, immunotherapy, biologic or targeted therapy) or radiation therapy for the current colon cancer except for one cycle of mFOLFOX6. **Cycle 1 of mFOLFOX6 must have been administered per [Appendix III](#).**

**3.2.4 Age  $\geq$  12 years****3.2.5 Performance Status:**

- Patients <16 years of age: Lansky  $\geq$  50%
- Patients 16 to <18 years of age: Karnofsky  $\geq$  50%
- Patients  $\geq$ 18 years of age: ECOG Performance Status  $\leq$  2

**3.2.6 Not Pregnant and Not Nursing**

This study involves: 1) an investigational agent whose genotoxic, mutagenic and teratogenic effects on the developing fetus and newborn are unknown; and 2) an agent that has known genotoxic, mutagenic, and teratogenic effects.

Therefore, for women of childbearing potential only, a negative pregnancy test done  $\leq$  7 days prior to registration is required.

A female of childbearing potential is a sexually mature female who: 1) has not undergone a hysterectomy or bilateral oophorectomy; or 2) has not been naturally postmenopausal for at least 12 consecutive months (i.e. has had menses at any time in the preceding 12 consecutive months).

**3.2.7 Required Initial Laboratory Values:**

Absolute Neutrophil Count (ANC)	$\geq 1500 \text{ mm}^3$
Platelet Count	$\geq 100,000 \text{ mm}^3$ *
Creatinine	$\leq 1.5 \times$ upper limit of normal (ULN)
or	
Calculated Creatinine Clearance	$\geq 45 \text{ mL/min}$ **
Total Bilirubin	$\leq 1.5 \times$ upper limit of normal (ULN)***
AST / ALT	$\leq 2.5 \times$ upper limit of normal (ULN)
TSH	WNL****

\* Platelets  $\geq 75,000$  required for patients who received Cycle 1 of mFOLFOX6 prior to registration

\*\* By Cockcroft-Gault equation. Alternatively, for patients < 18 years of age, maximum serum creatinine  $\leq$  the below age-sex-specific norms:

Creatinine (mg/dL)		
Age	Male	Female
12 years	1.2	1.2
13 to <16 years	1.5	1.4
16 to <18 years	1.7	1.4

\*\*\* Except in the case of Gilbert disease

\*\*\*\* Supplementation is acceptable to achieve a TSH WNL. In patients with abnormal TSH, if Free T4 is normal and patient is clinically euthyroid, patient is eligible.

### 3.2.8 Comorbid Conditions

No active known autoimmune disease, including colitis, inflammatory bowel disease (i.e. ulcerative colitis or Crohn's disease), rheumatoid arthritis, panhypopituitarism, adrenal insufficiency.

No known active hepatitis B or C.

- Active Hepatitis B can be defined as:
  - HBsAg detectable for > 6 months;
  - Serum HBV DNA 20,000 IU/ml (105 copies/ml); lower values 2,000-20,000 IU/ml (104-105 copies/ml) are often seen in HBeAg-negative chronic hepatitis B;
  - Persistent or intermittent elevation in ALT/AST levels;
  - Liver biopsy showing chronic hepatitis with moderate or severe necroinflammation.
- Active Hepatitis C can be defined as:
  - Hepatitis C AB positive, AND
  - Presence of HCV RNA

Excluded if known active pulmonary disease with hypoxia defined as:

- Oxygen saturation < 85% on room air, or
- Oxygen saturation < 88% despite supplemental oxygen

No grade  $\geq 2$  peripheral motor or sensory neuropathy.

Patients positive for HIV are eligible only if they meet all of the following:

- A stable regimen of highly active anti-retroviral therapy (HAART)
- No requirement for concurrent antibiotics or antifungal agents for the prevention of opportunistic infections
- A CD4 count above 250 cells/mcL, and an undetectable HIV viral load on standard PCR-based tests

### 3.2.9 Concomitant Medications

No other planned concurrent investigational agents or other tumor directed therapy (chemotherapy, radiation) while on study.

No systemic daily treatment with either corticosteroids (>10 mg daily prednisone equivalents) or other immunosuppressive medications within 7 days of registration.

### 3.2.10 Allergies

No known history of severe allergic anaphylactic reactions to chimeric, human or humanized antibodies, or fusion proteins.

No known hypersensitivity to CHO cell products or any component of the atezolizumab formulation.

No known allergy to 5-fluorouracil, oxaliplatin, or leucovorin.

#### 4.0 PATIENT REGISTRATION

##### 4.1 Investigator and Research Associate Registration with CTEP

Food and Drug Administration (FDA) regulations require sponsors to select qualified investigators. National Cancer Institute (NCI) policy requires all individuals contributing to NCI-sponsored trials to register with their qualifications and credentials and to renew their registration annually. To register, all individuals must obtain a Cancer Therapy Evaluation Program (CTEP) Identity and Access Management (IAM) account at <https://ctepcore.nci.nih.gov/iam>. Investigators and clinical site staff who are significant contributors to research must register in the [Registration and Credential Repository](#) (RCR). The RCR is a self-service online person registration application with electronic signature and document submission capability.

RCR utilizes five person registration types.

- Investigator (IVR)—MD, DO, or international equivalent;
- Non Physician Investigator (NPIVR)—advanced practice providers (e.g., NP or PA) or graduate level researchers (e.g., PhD);
- Associate Plus (AP)—clinical site staff (e.g., RN or CRA) with data entry access to CTSU applications such as the Roster Update Management System (RUMS), OPEN, Rave; acting as a primary site contact, or with consenting privileges
- Associate (A)—other clinical site staff involved in the conduct of NCI-sponsored trials; and
- Associate Basic (AB)—individuals (e.g., pharmaceutical company employees) with limited access to NCI-supported systems.

RCR requires the following registration documents:

Documentation Required	IVR	NPIVR	AP	A	AB
FDA Form 1572	✓	✓			
Financial Disclosure Form	✓	✓	✓		
NCI Biosketch (education, training, employment, license, and certification)	✓	✓	✓		
GCP training	✓	✓	✓		
Agent Shipment Form (if applicable)	✓				
CV (optional)	✓	✓	✓		

IVRs and NPIVRs must list all clinical practice sites and Institutional Review Boards (IRBs) covering their practice sites on the FDA Form 1572 in RCR to allow the following:

- Addition to a site roster;

- Selection as the treating, credit, or drug shipment investigator or consenting person in OPEN;
- Ability to be named as the site-protocol Principal Investigator (PI) on the IRB approval; and
- Assignment of the Clinical Investigator (CI) task on the Delegation of Tasks Log (DTL).

In addition, all investigators acting as the Site-Protocol PI (investigator listed on the IRB approval), consenting/treating/drug shipment investigator in OPEN, or as the CI on the DTL must be rostered at the enrolling site with a participating organization.

For questions, please contact the **RCR Help Desk** by email at [[contact]](mailto:[contact]).

